3.1 General Design

This is a phase II study that will deliver personalized radiation treatment plans by combining differential tumor dose escalation based on residual tumor SUV of mid-treatment FDG-PET/CT in select patients classified as early FDG PET non-responders, and functional pulmonary avoidance based on perfusion SPECT/CT. The long-term goal is to improve patient survival without increasing toxicity of treatment.

Trial schema is shown below in Figure 1. All patients will undergo imaging at 3 time points: 1) baseline FDG PET/CT and SPECT/CT for tumor imaging and functional lung avoidance treatment planning; 2) mid-radiation treatment (24 Gy nominal) FDG PET/CT to assess tumor response to therapy; 3) 3 months post-radiation FDG PET/CT and SPECT/CT, to assess cancer response to treatment and functional lung tissue response. Based on tumor response at the mid-treatment PET/CT, patients will either be classified as responders (receive 60 Gy per standard of care with functional lung avoidance), or non-responders (dose escalation to 74 Gy while keeping overall treatment constant at 30 fractions and avoiding functional lung). Follow up of all patients will also include standard of care evaluations (see Table 1 for study calendar).

**Figure 1. Clinical trial schema for FLARE RT.****Table 1. Study Calendar**

	Pre-screen	Baseline	Mid-RT	3-Months Post-RT	1-year Post-RT
		Prior to RT Start	20-30 Gy	2-4 mo.	9-18 mo.
Informed Consent		X			
Medical History	X			X	X
Physical Exam	X		X	X	X
ECOG Performance Status	X		X	X	X
Lab Work***	X				
Pulmonary Function Tests (PFTs) including FEV1	X			X	X
Brain CT or MRI	X				
¹⁸F-FDG PET/CT Scan#	X	X ^a	X ^c	X	
SPECT/CT with ^{99m}Tc-MAA and ^{99m}Tc-SULFUR COLLOID# performed at UWMC		X ^b	* ^b	X ^b	
Blood and urine collection for future correlative studies		X ^{**}	X ^{**}	X ^{**}	

X Required for study

* Optional for study

** Optional but highly encouraged

***CBC with absolute neutrophil count and platelet count; Serum chemistries include BUN, creatinine, sodium, potassium, bicarbonate, chloride, glucose, total protein, total bilirubin, AST, ALT, alkaline phosphatase, and albumin

Scans should ideally be performed in the treatment position with treatment immobilization

^a Baseline PET/CT scans will be done as part of routine clinical care for lung cancer staging and radiation treatment planning. For patients whose clinical scans are >1 month old or do not meet research scan quality standards, a repeat research PET/CT will be done around the time of simulation, which will be paid for by the study.^b All SPECT/CT scans performed will be paid for by the study.

^c Mid-Treatment PET/CT performed will be paid for by the study. Ideally, mid-RT PET/CT to be performed between treatment fraction #12 and #13 (~24 Gy).

3.2. Statistical Plan

The primary endpoint of the study will be 2-year overall survival (OS). The primary objective will be to test the superiority of the 2-year overall survival rate in patients enrolled on the FLARE RT trial compared to the 60 Gy cohort of RTOG 0617 (57% 2yr OS) for historical control (11). RTOG 0617 was a randomized phase III trial for patients with unresectable non-small cell lung cancer (NSCLC), testing two radiation doses (60 Gy versus 74 Gy), and addition of cetuximab to standard chemoradiation. Results of RTOG 0617 established the current standard of care for NSCLC: concurrent chemoradiation to 60 Gy.

The expected 2yr OS and effect size of FLARE RT was derived from a weighted average of mid-treatment FDG PET responders (2 yr. OS = 92%, 41% of patient population) and non-responders (2 yr. OS = 33%, 59% of patient population) identified in a prospective patient series with 2 yr. OS rate (56%) in strong agreement with the 60 Gy cohort of RTOG 0617 (23). Based on data from a dose escalation meta-analysis (10) and the University of Michigan experience tumor dose escalation to 74 Gy in non-responders are expected to produce 4% relative improvement in overall survival per Gy (3). Combined with functional lung avoidance to reduce mean perfused lung dose from 20 Gy to 10 Gy and risk of clinical grade radiation pneumonitis, we predict a 72% 2yr OS in patients receiving FLARE RT.

The FLARE RT trial features a non-randomized design that selectively assigns patients to one of two arms based on early treatment response assessment on FDG PET/CT. In order to assess whether this selection strategy leads to superior 2yr OS compared to the historical control, we will perform a one sample proportionality test using all patients who complete either FLARE RT treatment arm (standard dose arm in responders + dose escalation arm in non-responders). In our cohort of at least 49 patients, the test is expected to detect a 2yr OS rate improvement relative to historical control from 57% to 72%, under assumptions of 5% Type I error rate ($\alpha=0.05$), 80% power ($\beta=0.20$), and 1% margin of superiority ($\delta=0.01$).

Secondary objectives will feature a non-inferiority proportionality test of pulmonary toxicity incidence, defined as CTCAE v4 grade 2 or higher pneumonitis, between patients receiving FLARE RT and historical rates. Interim and final statistical analyses of the clinical endpoints (local control, progression-free survival, overall survival) will consist of Kaplan-Meier estimation and Cox proportional hazard regression. We will not conduct formal subset analyses due to insufficient statistical power. However, we will assess the relative strengths of hazard ratio estimates (and 95% confidence intervals) from a few predictors, including pre-treatment and mid-treatment imaging metrics extracted from PET/CT and SPECT/CT data. The degree of correlation amongst the variables will be evaluated. We will conduct linear regression of post-treatment lung perfusion SPECT/CT changes and decline in standard pulmonary function tests (FEV1,

DLCO, etc.). Lastly, we will perform ROC analysis to associate pre-treatment lung perfusion SPECT/CT parameters with dichotomous incidence of pneumonitis.

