**FRED HUTCHINSON CANCER RESEARCH CENTER
UNIVERSITY OF WASHINGTON SCHOOL OF MEDICINE**

**Personalized radiation therapy through functional lung avoidance and
response-adaptive dose escalation: utilizing multimodal molecular
imaging to improve the therapeutic ratio (FLARE RT)**

Principal Investigator: [name]
Associate Professor
Department of Radiation Oncology
University of Washington Medical Center
[name]
[name]
[contact]
[contact]
Email: [contact]

Co-Investigators: [name]
[name]
[name], PhD
[name]

Version date:

Protocol Amendment 4: version February 5, 2020

Study Summary

Title	Personalized radiation therapy through response-adaptive dose escalation and functional lung avoidance: utilizing multimodal molecular imaging to improve the therapeutic ratio (FLARE RT)
Short Title	FLARE RT
Protocol Number	CCIRB 9599
Phase	Phase II
Methodology	Single Arm Open-Label
Study Duration	5 yrs.
Study Center(s)	University of Washington Medical Center
Objectives	To utilize mid-treatment FDG PET/CT tumor response to select non-responding patients for dose escalation, while utilizing functional lung avoidance to mitigate toxicity. Changes in tumor FDG uptake on mid-treatment PET/CT (24 Gy nominal) will divide patients into “responders” and “non-responders”. Responders will receive 60 Gy to their tumor per standard of care; non-responders will undergo dose escalation to 74 Gy. All patients will receive functional lung avoidance radiation treatment via SPECT/CT imaging with ^{99m}Tc-MAA and ^{99m}Tc-SULFUR COLLOID to accurately identify and preferentially spare functional lung. Primary endpoint of this study will be 2-yr. overall survival.
Number of Subjects	The projected enrollment number is 60 in order to meet the study goal of 50 evaluable subjects.
Diagnosis and Main Inclusion Criteria	Patients diagnosed with stage IIB-III non-small cell lung cancer receiving definitive chemoradiation.
Study Product, Dose, Route, Regimen	All scans are FDA approved for use with patients: ^{18}FFDG-PET/CT and SPECT/CT with ^{99m}Tc-MAA and ^{99m}Tc-Sulfur Colloid
Duration of administration	Beyond standard of care imaging, some patients may undergo a repeat baseline protocol specific FDG-PET/CT, and be considered research, then a PET/CT mid-treatment, and 2 SPECT/CT scans (pre-treatment and 3 months post-treatment).

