The primary endpoint of the study will be 2 year overall survival. The primary objective will be to test the superiority of 2yr OS in the FLARE RT patient cohort over the 60 Gy cohort of RTOG 0617 (57% 2yr OS) for historical control. Based on an estimated improvement to 72% 2yr OS, we will enroll at least **49 patients** to test for superiority of FLARE RT at 80% power and 5% Type I error.

Secondary Objective

[figure not shown]
- CTCAE v4 grade 2 or higher pneumonitis incidence from FLARE RT compared to historical controls (non-inferiority test)
- 1 yr local control, progression-free survival, and pulmonary function test decline
- Identification of baseline FDG PET/CT and mid-treatment FDG PET/CT imaging biomarkers for predicting patient survival
- Identification of baseline perfusion SPECT/CT imaging biomarkers for predicting G2+ pneumonitis and PFT decline
- Collection of plasma and urine samples for future correlative studies between imaging biomarkers and cytokine biomarkers of radiation response in both tumor and normal tissue

3 Study Design

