5.8 Criteria for Removal/Withdrawal from Treatment

Patients will be withdrawn from treatment if their clinical conditions decline so they are no longer able to tolerate x-ray / proton radiation, or are unlikely to clinically benefit from further therapy.

Patients will still receive follow up care per standard of care even if they withdraw from the study. If a subject withdraws consent to participate in the study or aspects of the study, attempts will be made to obtain permission to record at least survival data up to 6 months post-treatment.

6 Systemic Therapy

All patients must receive cytotoxic (not targeted agents) systemic therapy concurrent with radiation, but exact agent and dosing are at discretion of medical oncology.

7 Data and Safety Monitoring Plan

Institutional support of trial monitoring will be in accordance with the FHCRC/University of Washington Cancer Consortium Institutional Data and Safety Monitoring Plan. Under the provisions of this plan, FHCRC Clinical Research Support coordinates data and compliance monitoring conducted by consultants, contract research organizations, or FHCRC employees unaffiliated with the conduct of the study. Independent monitoring

visits occur at specified intervals determined by the assessed risk level of the study and the findings of previous visits per the institutional DSMP.

In addition, protocols are reviewed at least annually and as needed by the Consortium Data and Safety Monitoring Committee (DSMC), FHCRC Scientific Review Committee (SRC) and the FHCRC/University of Washington Cancer Consortium Institutional Review Board (IRB). The review committees evaluate accrual, adverse events, stopping rules, and adherence to the applicable data and safety monitoring plan for studies actively enrolling or treating patients. The IRB reviews the study progress and safety information to assess continued acceptability of the risk-benefit ratio for human subjects. Approval of committees as applicable is necessary to continue the study.

The trial will comply with the standard guidelines set forth by these regulatory committees and other institutional, state and federal guidelines.

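### The primary objective is about patients enrolled, but the primary test counts only those who complete treatment; this tilts 2-year survival upward by an amount the plan does not bound

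*Combined protocol and SAP*

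**What the plan says.** Section 3.2 describes two populations for one test. The objective is "superiority of the 2-year overall survival rate in patients enrolled on the FLARE RT trial", and section 2 likewise speaks of "superiority of 2yr OS in the FLARE RT patient cohort". Two paragraphs further on in section 3.2, the analysis is stated as "we will perform a one sample proportionality test using all patients who complete either FLARE RT treatment arm".

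Three other places bear on the point:

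- **Study Summary, Number of Subjects:** "The projected enrollment number is 60 in order to meet the study goal of 50 evaluable subjects". Neither evaluability nor completion is defined anywhere.
- **Section 5.8, stopping treatment:** "Patients will be withdrawn from treatment if their clinical conditions decline so they are no longer able to tolerate x-ray / proton radiation". Being unlikely to benefit from further therapy is the other ground.
- **Section 5.8, withdrawal of consent:** "attempts will be made to obtain permission to record at least survival data up to 6 months post-treatment". The primary endpoint is at 2 years.

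The secondary part of section 3.2 plans Kaplan-Meier and Cox analyses of overall survival but names no population for them. The documents contain no all-enrolled analysis, no rule that counts non-completers as failures, and no cap on non-completion.

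**The concern.** Completing an arm is itself an outcome. Sections 3.1 and 5.1 assign arms only after the mid-treatment PET, and treatment runs to 30 fractions. On a literal reading, a patient who dies or stops before the scan belongs to no arm, and one who stops in weeks 4 to 6 has not completed. A completer must survive about six weeks and stay well enough to be treated.

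A death during treatment is a certain failure at 2 years, so removing it can only raise the observed rate. Patients withdrawn for decline are likely, though not certain, to do worse than average. Patients who cannot tolerate the escalated plan would also be left out of the primary comparison, although their outcomes belong to the strategy under test.

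A single-arm design offers no offset, because no concurrent arm undergoes the same exclusion. The documents describe the 57% benchmark without any completion restriction. That it is unrestricted is an inference from their silence.

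At stake is the denominator of the only primary test. Left open, it also allows the analysis set to be settled after survival is known.

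**Working it through.** **The plan's own figures.** The plan gives no figure for the number or survival of non-completers, so there is none to reproduce on this exact point. Its sample size of 49 matters only as background. The one-sided formula n = p1(1−p1)[(z_α+z_β)/d]² with p1 = 0.72 gives 63.6 (so 64) for d = 0.72 − 0.57 − 0.01 = 0.14. It gives 48.7 (so 49) only for d = 0.16, that is, with the margin's sign reversed. That is a separate matter, but it explains why the baseline power below is under 80%.

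**Inputs from the documents.** Null 57%, target 72%, alpha 5%, margin 1% (section 3.2); 60 enrolled for 50 evaluable (Study Summary).

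**Assumptions.** One-sided exact binomial test (sidedness is not stated); 50 completers; true 2-year survival of 57% in all treated patients; survival q among the excluded of 40, 30 or 20%, with 0% for deaths during treatment.

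**Decision rules for 50 completers.**
- Null 57%, no margin: success at ≥35/50; type I error 4.2%.
- Null 58%, with the 1% margin: success at ≥36/50; type I error 2.1% at a true 57%.

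**Bias.** With x the share excluded, completer survival = (0.57 − x·q)/(1 − x). Example, 10 of 60 with q = 30%: (0.57 − 0.1667 × 0.30)/0.8333 = 0.624, a bias of 5.4 points. Type I error is then P(X ≥ 35) or P(X ≥ 36) with n = 50 at that rate.

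| Excluded | q | Bias (points) | Type I error, no margin | Type I error, 1% margin |
|---|---|---|---|---|
| 2 of 52 | 40 / 30 / 20% | 0.7 / 1.1 / 1.5 | 5.1 / 5.7 / 6.4% | 2.6 / 3.0 / 3.4% |
| 2 of 52 | 0% | 2.3 | 7.9% | 4.4% |
| 5 of 55 | 40 / 30 / 20% | 1.7 / 2.7 / 3.7 | 6.8 / 8.8 / 11.4% | 3.7 / 4.9 / 6.6% |
| 10 of 60 | 40 / 30 / 20% | 3.4 / 5.4 / 7.4 | 10.6 / 16.8 / 25.1% | 6.0 / 10.3 / 16.5% |
| any | 57% | 0 | 4.2% | 2.1% |

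**Where the low scenario comes from.** A constant hazard giving 57% at 2 years implies 1 − 0.57^(6/104) = 3.2% dying within six weeks, or 0.032 × 52 ≈ 1.7 patients. Withdrawals for decline would add to that. The 10 of 60 row is the most the Summary's allowance could give, and only if all ten are poor-prognosis non-completers.

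**A single result.** The smallest success without the margin, 35/50 (70.0%, p = 0.042), becomes 35/60 (58.3%, p = 0.47) if ten excluded patients all died.

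**The case against.** The strongest case for leaving this as a minor wording matter has five parts.

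1. **The margin.** The test as written carries a 1% margin. With it, the scenario nearest to the documents (2 of 52) stays below 5% even if both excluded patients died, and 5 of 55 exceeds 5% only at 20% survival. This stands as a limit on size. The error still rises from 2.1% to as much as 4.4% with only two exclusions, and nothing in the plan limits exclusions to two.
2. **The 60-versus-50 allowance.** It may cover ineligibility, never starting, an unusable scan or loss to follow-up. This also stands: 10 of 60 is an upper case, not an expectation.
3. **A milder reading.** The sentence may be meant chiefly to say that both arms are pooled, with completion used loosely. If so, the plan should say so; as written, the sentence excludes non-completers.
4. **The prospective series.** The series cited in section 3.2 was classified by mid-treatment PET and had 56% 2-year survival, close to the benchmark, so reaching the scan may not raise survival much. This is a cross-study comparison and says nothing about stopping in weeks 4 to 6.
5. **Other safeguards.** The grade 5 stopping rule in section 7.1 and the Kaplan-Meier analyses mean that early deaths are not invisible. Neither puts them back into the primary denominator.

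**Conclusion.** The concern holds and should be corrected before the primary analysis. The mismatch between enrolled and completing patients is in the text of section 3.2, and no other section resolves it. The upward direction is structural for deaths during treatment and well supported for withdrawals, given the grounds in section 5.8. It vanishes only if non-completers survive as well as everyone else.

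The size cannot be fixed from the documents. Across the assumed range it runs from under 1 point to 7.4 points, against a planned effect of 15 points (57% to 72%). Confidence in the size is moderate, because it rests on assumed numbers and survival of non-completers, an assumed one-sided exact test, and a benchmark whose own patient set is not described.

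**What to change.** In section 3.2, name one primary analysis set: all eligible registered patients who start protocol radiation, whether or not they complete it or reach the mid-treatment PET. State that survival is measured from the start of radiation (or registration). Define completion and report completers as a sensitivity analysis. Bring the objective's wording and the Summary's term evaluable into line with this set. Seek 2-year vital status for all non-completers; for patients who withdraw consent, section 5.8 currently seeks at least 6 months. No clinical rule for stopping treatment needs to change.

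The cost is protocol and SAP wording plus the extra follow-up. There is no gain in power. If 72% holds only among completers, and the others survive at 40, 30 or 20%:

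| Set analysed | Overall 2-year survival | Power, no margin | Power, 1% margin |
|---|---|---|---|
| 50 completers only | 72% | 69% | 57% |
| All 52 | 70.8 / 70.4 / 70.0% | 66 / 64 / 61% | 54 / 52 / 50% |
| All 60 | 66.7 / 65.0 / 63.3% | 45 / 35 / 25% | 35 / 25 / 17% |

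If 72% holds in all 60 treated patients, power without the margin is 78%. The sample size should therefore be rechecked with the target rate stated for the full set. In return, type I error at a true 57% is about 4.9% (≥36/52 or ≥41/60), or 2.6 to 2.7% with the margin (≥37/52 or ≥42/60), whatever the survival of non-completers.

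### The primary 2-year survival test needs vital status at 24 months, scheduled follow-up ends at 1 year, and no rule covers patients censored in between

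*Combined protocol and SAP*

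**What the plan says.** Section 3.2 (Statistical Plan) makes 2-year overall survival primary and attaches one test to it: "we will perform a one sample proportionality test using all patients who complete either FLARE RT treatment arm". The null rate is 57% and the target 72%, with 5% type I error, 80% power, at least 49 patients and a "1% margin of superiority". Sidedness is not stated.

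The next paragraph of Section 3.2, which opens with the secondary objectives, adds: "Interim and final statistical analyses of the clinical endpoints (local control, progression-free survival, overall survival) will consist of Kaplan-Meier estimation", together with Cox regression. It does not link that estimate to the 57% comparison.

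On follow-up, the last column of Table 1 (Study Calendar) is the 1-year visit after radiotherapy, with a window of 9 to 18 months. Section 5.8 says that after withdrawal of consent "attempts will be made to obtain permission to record at least survival data up to 6 months post-treatment". The Study Summary plans 60 enrolled for 50 evaluable subjects and does not define evaluable. Neither document section gives a 24-month vital-status check, an expected loss rate, or a rule for a patient whose 24-month status is unknown.

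**The concern.** A one-sample proportion test takes one yes-or-no value per patient. A patient last known alive at, say, 14 months has no such value at 24 months, so the analyst must drop the patient or assign a status. Dropping removes people who had survived so far while keeping all recorded early deaths, which pulls the estimate down. Counting them alive pushes it up, and counting them dead pushes it down further. Kaplan-Meier uses the follow-up that each patient did contribute and avoids the choice, provided censoring is unrelated to prognosis.

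The trial is open-label with a single comparison against a fixed rate. An unwritten scoring rule could therefore be settled after the outcomes are known, and with about 50 patients a few unknowns can decide the result.

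**Working it through.** **The plan's own figure.** For a one-sample proportion with the variance at the target rate, n = p1(1−p1) × [(z_α + z_β)/(p1 − p0 − δ)]². With p1 = 0.72, p0 = 0.57, δ = 0.01 and one-sided 5%: 0.2016 × (2.487/0.14)² = 63.6, so 64. The stated 49 appears only with the margin's sign reversed: 0.2016 × (2.487/0.16)² = 48.7. That is a separate matter. What counts here is that this formula has no term for censoring, so the size calculation takes every status as known.

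**Assumptions.** The documents give no loss rate. I assume exponential survival and that a fraction f of patients (5% or 10%) has a censoring time uniform over 1 to 24 months, independent of survival. Tests are exact binomial against 57%, one-sided 5%, n = 50.

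**Expected estimates at a true rate of 72%.** λ = −ln(0.72)/24 = 0.01369 per month. The mean of S(t) over 1 to 24 months is (e^−λ − e^−24λ)/(23λ) = 0.2664/0.3148 = 0.846. The fraction actually censored before 24 months is f × 0.846.

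| Quantity | f = 5% | f = 10% |
|---|---|---|
| Censored | 4.2% | 8.5% |
| Counted dead: 0.72(1−f) | 68.4% | 64.8% |
| Dropped: 0.72(1−f)/(1−0.846f) | 71.4% | 70.8% |
| Counted alive: 0.72(1−f)+0.846f | 72.6% | 73.3% |
| Kaplan-Meier (simulated mean) | 72.0% | 72.0% |

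**Chance of success at a true 72%, n = 50.** With nobody censored, success needs at least 35 alive, and power is 69% for both the exact test and Kaplan-Meier (Greenwood, log(−log) scale). With censoring, the proportion tests follow from the binomial and Kaplan-Meier from 40,000 simulated trials:

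| Handling | f = 5% | f = 10% |
|---|---|---|
| Counted dead | 47% | 27% |
| Dropped | 60% | 56% |
| Counted alive | 72% | 76% |
| Kaplan-Meier | 67% | 66% |

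**Type I error at a true 57%, n = 50.** The same formula gives a mean S(t) of 0.755, so 3.8% and 7.6% are censored. The exact test's error is 4.2% with nobody censored. Counting the censored alive gives 5.5% and 7.1%. Dropping gives 2.8% and 2.3%. Kaplan-Meier gives 4.4% and 3.9%.

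At n = 49 the exact test is more conservative (2.7% with nobody censored). Counting alive then gives 3.6% and 4.8%, still below 5%; about 15% censored takes it to 8.7%. At that size Kaplan-Meier has 72% power against 61% even without loss, because the exact test is discrete. I therefore use n = 50 to isolate the effect of censoring.

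**How few patients matter (hypothetical).** N = 49, two censored, 34 of the other 47 alive. Exact one-sided p against 57%:
- counted dead, 34/49 (69.4%): 0.052
- dropped, 34/47 (72.3%): 0.022
- counted alive, 36/49 (73.5%): 0.013

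Against 58%, if the margin is added to the null, these are 0.069, 0.031 and 0.018. With a score test against 57%, two patients are not enough (34/49 gives 0.040). Three are: 33/49 gives 0.072, 33/46 gives 0.022 and 36/49 gives 0.010.

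**The case against.** The strongest reply is that Section 3.2 is clear about what decides. Alpha, power and sample size are all attached to the proportion test, and the Kaplan-Meier sentence covers three endpoints together without naming a comparison. That stands. A reader might infer that the section contradicts itself or leaves the deciding analysis open. It does not: a named primary test alongside survival curves is a common arrangement.

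A reader might also infer that the plan expects censoring. The documents do not support that either. The 6 months in Section 5.8 is a minimum, and it concerns consent withdrawals. Patients who leave during treatment are already outside a set defined by completing treatment. A 5-year study duration leaves room for about three years of accrual plus two of follow-up, and nothing schedules the analysis before the last patient reaches 24 months. What remains is that the calendar ends at 9 to 18 months and nothing secures 24-month status. That makes early censoring of some completers plausible but does not establish it.

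The size is also open to challenge. The loss rates are mine. Dropping moves the estimate by only about half a point at 4% censored, and its error is conservative. The p-value example turns on counting the censored dead, which the plan does not propose. All of this stands and limits the point to lost power and an unwritten rule. Finally, Kaplan-Meier looks unbiased here because censoring was simulated as independent; if loss tracks prognosis, it is biased too. An exact test with full 24-month ascertainment would be an equally sound design.

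**Conclusion.** The point holds in conditional form. The deciding test requires 24-month vital status, the plan neither schedules its collection nor says how unknown status is scored, and Kaplan-Meier is listed without a role in the primary comparison.

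If about 4 to 8% of 50 patients are censored early and independently, the choice of scoring spreads the estimate from about 65 to 73% around a true 72%. Dropping costs roughly 7 to 10 points of power relative to Kaplan-Meier (60 against 67, 56 against 66). Counting the censored alive takes one-sided type I error modestly above 5% at n = 50, though not at n = 49. Two unknown patients can change an exact-test conclusion in a close result.

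These sizes rest on assumed loss rates, exponential survival and a one-sided test. With complete 24-month status the point estimates coincide and the problem disappears. It would be wrong to conclude that the primary result will be biased, or that a proportion test is invalid in itself.

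**What to change.** In Section 3.2, name the Kaplan-Meier estimate of overall survival at 24 months, with Greenwood variance on the log(−log) scale, as the single deciding analysis. Test it against the same null as the present test, and say whether that null is 57% or includes the 1% margin. Keep the exact proportion test as a sensitivity analysis, run once with censored patients all scored dead and once all scored alive.

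This changes wording only and uses a method the section already lists. At n = 50 it loses no power if follow-up proves complete (69% either way). It has three costs: a large-sample test replaces an exact one, censoring must be assumed unrelated to prognosis, and the power statement, written for the proportion test, must be restated. A vital-status check at 24 months is not part of this wording change, but it would reduce reliance on the second assumption and keep enough patients at risk near 24 months.

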Statistical Methodology	Primary endpoint of the study will be 2 yr. overall survival, compared to the 60 Gy cohort of RTOG 0617 (57% 2yr OS). With an estimated improvement to 72% 2yr OS, we will need 49 patients to test for superiority of FLARE RT at 80% power and 5% Type I error. Secondary endpoints will include toxicity, and in particular CTCAE v4 grade 2 or higher pneumonitis, and 1 yr. local control, progression-free survival, and pulmonary function test decline. We will also collect plasma and urine for future correlative studies.
-------------------------	--

Table of Contents

1. Introduction
 - 1.1. Background
 - 1.2. Local Control Impacts Survival in Locally Advanced NSCLC
 - 1.3. Radiation Dose Escalation Can Improve Local Control in NSCLC, but Uniform Dose Escalation Is Detrimental
 - 1.4. FDG PET/CT Can Select For Patients at High Risk of Local Failure and Guide Dose Escalation
 - 1.5. Radiation to the Lungs Causes Pulmonary Toxicity and Limits the Deliverable Dose
 - 1.6. Current Radiation Planning Methods are Unable to Accurately Predict Which Patients Will Develop Pulmonary Toxicity
 - 1.7. SPECT/CT Perfusion/Ventilation Scans can Detect Heterogeneity in Lung Function
2. Study Objectives
3. Study Design
 - 3.1. General Design
 - 3.2. Statistical Plan
 - 3.3. Eligibility
4. Study Registration
5. Radiation Therapy
 - 5.1. Dose Specifications
 - 5.2. Localization, simulation and immobilization
 - 5.3. Target Volumes
 - 5.4. Critical Structures
 - 5.5. Treatment Planning
 - 5.6. Radiation Quality Assurance Reviews
 - 5.7. Radiation Toxicity
 - 5.8. Criteria for Removal/Withdrawal from Treatment
6. Systemic Therapy
7. Data and Safety Monitoring Plan
 - 7.1. Early Stopping Rules
 - 7.2. Interim Data Review
8. Data Management/Confidentiality

1 Introduction

This document is a protocol for a human research study. This study is to be conducted according to US and international standards of Good Clinical Practice (FDA Title 21 part 312 and International Conference on Harmonization guidelines), applicable government regulations and Institutional research policies and procedures.

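### 49 to 50 evaluable patients do not give the stated 80% power for 57% versus 72% two-year survival; one-sided power is about 57% to 76%

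*Combined protocol and SAP*

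**What the plan says.** The primary endpoint is two-year overall survival, tested against a fixed 57% taken from the 60 Gy cohort of RTOG 0617, with 72% expected under FLARE RT. The sample-size claim appears in three places:

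- Study Summary, Statistical Methodology: "we will need 49 patients to test for superiority of FLARE RT at 80% power and 5% Type I error".
- Section 2, Primary Objective: at least 49 patients "to test for superiority of FLARE RT at 80% power and 5% Type I error".
- Section 3.2: "In our cohort of at least 49 patients, the test is expected to detect a 2yr OS rate improvement relative to historical control". The two rates given there are 57% and 72%, with 5% type I error, 80% power and a "1% margin of superiority".

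Section 3.2 gives the analysis as follows: "we will perform a one sample proportionality test using all patients who complete either FLARE RT treatment arm". The objective in the same section is worded differently, as the "2-year overall survival rate in patients enrolled on the FLARE RT trial compared to the 60 Gy cohort of RTOG 0617". On numbers, the Study Summary says: "The projected enrollment number is 60 in order to meet the study goal of 50 evaluable subjects".

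The plan does not say whether the 5% is one-sided or two-sided, which form of one-sample test is meant (Wald, score or exact), or whether the margin moves the null from 57% to 58%.

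**The concern.** For a one-sample comparison of 57% with 72%, 49 looks too few under any usual formula, and a superiority margin should raise the number further. This is the only primary test. If its power is overstated, a negative result will be read as stronger evidence against the strategy than it is. Section 1.1 says the results are meant to support a multi-centre trial, so that reading has consequences.

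The unstated choices matter too. With about 50 patients, the choice of null and test form moves the number of survivors needed for success. If it is left open until the data are known, the same result could be called positive or negative. The error does not by itself affect safety.

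**Working it through.** **Inputs, all from Section 3.2 and the Study Summary.** Null p0 = 0.57, or 0.58 if the 1% margin is added; alternative p1 = 0.72; alpha = 0.05, sidedness not stated; power 0.80; 49 patients as the minimum and 50 evaluable as the goal.

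**Formulas.** With d = p1 − p0, z_β = 0.842, and z_α = 1.645 one-sided or 1.960 two-sided:

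- Variance at 72% (Wald): N = p1(1 − p1)(z_α + z_β)² / d²
- Null variance for the critical value (score): N = [z_α√(p0(1 − p0)) + z_β√(p1(1 − p1))]² / d²

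**Where 49 comes from.** One-sided, p1(1 − p1)(z_α + z_β)² = 0.2016 × (1.645 + 0.842)² = 1.2464. Dividing by 0.16² gives 48.7, so 49. A difference of 0.16 is 72% against 56%, not 57%. That could be the margin entered with the wrong sign (57% − 1%) or the 56% in the "prospective patient series with 2 yr. OS rate (56%) in strong agreement with the 60 Gy cohort of RTOG 0617". The documents do not show which. Neither is a test of superiority over 57%.

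**N for 80% power with the stated inputs.**

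| | Variance at 72% | Null variance |
|---|---|---|
| One-sided, null 57% | 1.2464/0.15² = 55.4 → 56 | 63.2 → 64 |
| One-sided, null 58% | 1.2464/0.14² = 63.6 → 64 | 72.2 → 73 |
| Two-sided, null 57% | 70.3 → 71 | 80.8 → 81 |
| Two-sided, null 58% | 80.7 → 81 | 92.3 → 93 |

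The one-sided exact binomial test first reaches 80% at 68 patients (null 57%) or 75 (null 58%).

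**One-sided power at the planned size.**

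| n, null | Variance at 72% | Null variance | Exact (alive needed; size) |
|---|---|---|---|
| 49, 57% | 75.6% | 70.0% | 60.6% (≥35; 2.7%) |
| 49, 58% | 70.5% | 64.6% | 60.6% (≥35; 3.7%) |
| 50, 57% | 76.3% | 70.8% | 68.8% (≥35; 4.2%) |
| 50, 58% | 71.2% | 65.4% | 57.1% (≥36; 2.9%) |

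The range is 57.1% to 76.3%. Arcsine, continuity-corrected, logit, complementary log-log and one-sample log-rank versions all fall inside it. At two-sided 5%, the formulas and exact tests run from 44.7% (exact, n = 50, null 58%) to 65.6% (variance at 72%, n = 50, null 57%).

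**Type I error that 80% power would require.** By the two normal formulas at 49 to 50 patients, one-sided alpha would have to be 6.4% to 8.7% against 57%, or 8.6% to 11.1% against 58%.

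**Cut-offs at n = 50, one-sided.** The Wald rule against 57% needs 34 alive, because (0.68 − 0.57)/√(0.68 × 0.32/50) = 1.67, above 1.645. The score and exact rules against 57% need 35. The exact rule against 58% needs 36. The Wald rule with 34 has 78.7% power, but its true size is 7.5%.

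**If all 60 enrolled were analysed.** One-sided power against 57% would be 82.7% (variance at 72%), 78.1% (null variance) and 78.4% (exact, ≥41). Against 58% it would be 78.0%, 72.8% and 69.3% (exact, ≥42).

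**The case against.** The arithmetic was not disputed. The best case for the plan has four parts.

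- **49 is a minimum and 60 will be enrolled.** This does not rescue the figure. The test is in completers and the goal is 50 evaluable. Even with all 60 analysed, 80% is reached only one-sided, without the margin and by the most favourable formula, and only if non-completers also survive at 72%.
- **The closest case is 1.3 points short.** The Wald rule at 50 patients has 78.7% power against 57%, but it spends 7.5% one-sided, not 5%. It is fair to add that the low end of the range (57%) owes something to the discreteness of the exact test, whose actual size there is 2.9%, and that the range mixes formula power with exact power. No entry that holds 5% comes near 80%.
- **This is a pilot-scale trial, and overstated power does not raise the false-positive rate.** That is true of the power alone. The undefined cut-off is different: choosing between 34, 35 and 36 survivors after seeing the data can raise it.
- **A simple count needs two-year status on every patient analysed.** This stands, and any repair has to deal with it. The study calendar ends at 9 to 18 months after radiotherapy. Section 5.8 seeks survival data only to 6 months after treatment from patients who withdraw consent. Section 3.2 plans Kaplan-Meier estimation for survival without saying how it relates to the proportion test.

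**Conclusion.** The concern holds. With the plan's own inputs, 49 to 50 evaluable patients do not give 80% power for superiority over 57% at 5% type I error, with or without the 1% margin. One-sided power is about 57% to 76%, so a true 72% would be missed in 24% to 43% of trials (21% with the oversized Wald rule) against the stated 20%. Two-sided power is about 45% to 66%.

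This assumes a one-sample test in 49 to 50 evaluable completers with known two-year status and a true rate of 72%. It does not depend on how 49 arose; the 72% against 56% explanation is an inference. Because the figure supports the only primary test, is stated three times, and leaves the success cut-off undefined, it must be corrected.

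**What to change.** Keep the planned 49 to 50 evaluable patients. In the Study Summary, Section 2 and Section 3.2, replace the 80% with the power of a named test. State the sidedness of alpha (the sponsor's choice), whether the null is 57% or 58%, the test form, and the critical count, with the rule for recalculating it if the number evaluable differs. For the exact binomial test in 50 evaluable patients the options are:

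| Test | Null | Alive at 2 years for success | Upper-tail size | Power at 72% |
|---|---|---|---|---|
| One-sided 5% | 57% | at least 35 | 4.2% | 68.8% |
| One-sided 5% | 58% | at least 36 | 2.9% | 57.1% |
| Two-sided 5% | 57% | at least 36 | 2.1% | 57.1% |
| Two-sided 5% | 58% | at least 37 | 1.4% | 44.7% |

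The two rows against 57% drop the margin; if one of them is chosen, remove the margin from Section 3.2.

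Suggested text for the first row: *The primary analysis is a one-sided 5% exact binomial test against 57% in 50 evaluable patients. Superiority is declared if at least 35 are alive at two years (size 4.2%; power 68.8% if the true rate is 72%).*

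Section 3.2 should also name one analysis population, since its objective refers to enrolled patients and its test to completers, and say how a patient without two-year status is handled.

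This is a wording change in three places with no added patients; the cost is a less favourable stated power. For information only, restoring one-sided 80% power would take about 56 to 75 evaluable patients, or 68 to 90 enrolled at the planned 50-of-60 rate (56 × 1.2 = 67.2; 75 × 1.2 = 90), which is 8 to 30 more than planned. Exact power is not monotone in n: it stays above 80% only from 74 evaluable against 57% (89 enrolled) or 81 against 58% (98 enrolled).
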